### Study Design:

This is a Phase I/II, open-label, multi-center, dose escalation study to estimate the MTD (or MAD) of SEL24/MEN1703 in patients with AML. At the end of Part 1 a RD of SEL24/MEN1703 has to be selected for further evaluation in Part 2. In Part 2 the safety and anti-leukemic activity of SEL24/MEN1703 will be further assessed in the study population.

SEL24/MEN1703 is taken orally once daily (QD) for 14 consecutive days over a 21-day treatment cycle.

**NOTE: At the time this protocol Version 12.0 is running, Part 1 has been completed. Procedures to be followed along Part 1 are reported below for completeness**

**Part 1** was initially designed with an accelerated titration design (ATD) for the first 4 cohorts. The study design has then been revised to follow a 3+3 design from Cohort 2 (50mg) onwards in order to assess for DLT, adverse events and adequate PK profile data from at least 3 patients in each dose level (see Table 3). Patients will be enrolled to cohorts in a sequential fashion following the dosing regimen and will be observed for safety and tolerability during Cycle 1, prior to permitting dose escalation to the next dose level (cohort). From Cohort 4 onwards there will be a mandated recruitment interval of at least 7 days for each patient enrolled.

Should a patient experience a toxicity which qualifies as a DLT during Cycle 1 in any cohort, that cohort will be expanded to enroll up to a maximum of 6 patients to further assess for toxicity prior to considering the next dosing step.

Cohort 4 (100mg) repeated twice due to the introduction of a new formulated SEL24/MEN1703 IMP. To distinguish between the original cohort and the repeat cohort at the same dose level, the repeat cohort is named Cohort 4F.

No recruitment interval is applied in the Cohort 4F where formulated SEL24/MEN1703 IMP is introduced, as this dose level has already been explored with the non-formulated SEL24/MEN1703 API in capsules. Upon the successful completion of the repeat Cohort 4F with the formulated IMP, the study will progress to the next Cohort 4b and onwards, according to the study design, using SEL24/MEN1703 formulated IMP only. In particular it has been shown that, overall, PK disposition of SEL24/MEN1703 (absorption, distribution and elimination) following the administration of formulated IMP is in line with that observed with non-formulated IMP. This evidence further supports that no dose adjustment is warranted with formulated IMP.

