## APPENDIX D: AML RESPONSE CRITERIA

Category	Definition	Comment
Response#		
CR without minimal residual disease (CR MRD -)	If studied pretreatment, CR with negativity for a genetic marker by RT-qPCR, or CR with negativity by MFC	Sensitivities vary by marker tested, and by method used; therefore, test used and sensitivity of the assay should be reported; analyses should be done in experienced laboratories (centralized diagnostics)
Complete remission (CR)	Bone marrow blasts <5%; absence of circulating blasts and blasts with Auer rods; absence of extramedullary disease; ANC $\geq 1.0 \times 10^9/L$ (1000/ $\mu$ L); platelet count $\geq 100 \times 10^9/L$ (100 000/ $\mu$ L)	MRD + or unknown
CR with incomplete hematologic recovery (CRi)	Bone marrow blasts <5%; absence of circulating blasts and blasts with Auer rods; absence of extramedullary disease with incomplete recovery of peripheral blood counts (ANC < $1.0 \times 10^9/L$ [1000/ $\mu$ L] or platelet count < $100 \times 10^9/L$ [100 000/ $\mu$ L])	
CR with partial hematologic recovery (CRh) 	Bone marrow blasts <5%; absence of circulating blasts and blasts with Auer rods; absence of extramedullary disease with partial recovery of peripheral blood counts (ANC > $0.5 \times 10^9/L$ [500/ $\mu$ L] and platelet count > $50 \times 10^9/L$ [50 000/ $\mu$ L])	
Morphologic leukemia-free state (MLFS)	Bone marrow blasts <5%; absence of blasts with Auer rods; absence of extramedullary disease; no hematologic recovery required	Marrow should not merely be “aplastic”; at least 200 cells should be enumerated or cellularity should be at least 10%
Partial remission (PR)	All hematologic criteria of CR; decrease of bone marrow blast percentage to 5% to 25%; and decrease of pretreatment bone marrow blast percentage by at least 50%	Especially important in the context of phase 1-2 clinical trials
Treatment failure		

Primary refractory disease	No CR or CR i after 2 courses of intensive induction treatment; excluding patients with death in aplasia or death due to indeterminate cause	Regimens containing higher doses of cytarabine are generally considered as the best option for patients not responding to a first cycle of 7+3; the likelihood of responding to such regimens is lower after failure of a first

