5.4.2. Secondary endpoints

Study Part 1:

- The number and frequency of AEs, safety laboratory, vital signs and ECG assessments

Study Part 1 and 2:

- Disease assessment will involve evaluation of leukemic blast proportion in the bone marrow. Hematologic parameters from the routine local assessments including blast percentage (where applicable), platelet count, and other relevant parameters such as transfusion dependence will also contribute to this assessment. Disease assessment will also include an aliquot of bone marrow aspirate/biopsy that will be centrally stored for future analysis (e.g. minimal residual disease), if any.
- Overall response rate (ORR), defined as the proportion of patients who have a complete remission (CR), complete remission with incomplete hematologic recovery (CRI), complete remission with partial hematologic recovery (CRh) or morphologic leukemia-free state (MLFS) response to therapy.
- Partial remission (PR) rate, defined as the proportion of patients who have a partial remission response to therapy.
- Duration of response (DoR), defined as the time from the date of first CR, CRI, CRh, CRMRD-, MLFS or PR until the date of documented relapse of any type, progressive disease or death due to disease progression for subjects who achieve CR, CRI, CRh, CRMRD-, MLFS or PR. Subjects who either do not relapse or die without report of relapse are considered nonevents and censored at their last relapse-free disease assessment date. Subjects who undergo an allogeneic HSCT will be considered non events and censored at the time of HSCT

- Relapse free survival (RFS), defined as the time from the date of first CR, CRi, CRh or CRM RD- until the date of documented relapse or death from any cause. Subjects who either do not relapse or do not die are censored at their last relapse-free disease assessment date.
- Event free survival (EFS), defined as the time from the date of first study drug intake until the date of documented relapse, treatment failure or death from any cause. For a subject who did not experience the event, EFS is censored at the date of last relapse-free disease assessment. Subject is not censored at HSCT.
- Overall survival (OS), defined as the number of days between the first study drug administration and death from any cause. Patients without the event are censored at the last date of follow-up.

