11.3. Data imputation

The missing values will not be imputed because, for all the analyses, an observed-cases approach will be applied.

Regarding time-to-event variables analysis:

- OS, if a subject is censored with respect to the event of interest the censoring date is defined as the date of the last performed visit;
- RFS, EFS and DoR, if a subject is censored with respect to the event of interest the censoring date is defined as the date of the last relapse/progression/event-free disease assessment.

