12.1. Efficacy analysis

The Overall Survival (OS) is calculated as:

- In case of all-cause death:
 $OS = date\ of\ death - date\ of\ first\ study\ drug\ administration + 1;$
- In case of censored information not for drop-out:
 $OS = date\ of\ end\ of\ observation\ period\ (i.e.\ study\ end / end\ of\ survival\ follow-up) - date\ of\ first\ study\ drug\ administration + 1;$
- In case of censored information for drop-out:
 $OS = last\ date\ known\ alive - date\ of\ first\ study\ drug\ administration + 1.$

The Relapse Free Survival (RFS) is calculated as:

- In case of relapse or all-cause death:
 $RFS = date\ of\ relapse\ or\ death\ (whichever\ comes\ first) - date\ of\ first\ CR,\ CRi,\ CRh\ or\ CR_{MRD-} + 1;$
- In case of censored information:
 $RFS = date\ of\ last\ relapse-free\ disease\ assessment - date\ of\ first\ CR,\ CRi,\ CRh\ or\ CR_{MRD-} + 1.$

The Event Free Survival (EFS) is calculated as:

- In case of relapse, treatment failure or all-cause death:
 $EFS = date\ of\ relapse,\ disease\ progression,\ treatment\ failure\ (failure\ to\ achieve\ CR/CRh/CRi/CR_{MRD-}\ after\ at\ least\ five\ cycles\ of\ treatment)\ or\ death\ (whichever\ comes\ first) - date\ of\ first\ study\ drug\ administration + 1;$
- In case of censored information:
 $EFS = date\ of\ last\ relapse-free/treatment-failure-free/progression-free\ disease\ assessment - date\ of\ first\ study\ drug\ administration + 1.$

The Duration of Response (DoR) is calculated as:

- In case of relapse, progressive disease or death due to progressive disease:
 $DoR = date\ of\ relapse\ of\ any\ type/progressive\ disease/death\ due\ to\ progressive\ disease - date\ of\ first\ CR,\ CRi,\ CRh,\ CR_{MRD-},\ MLFS\ or\ PR + 1;$
- In case of censored information:
 $DoR = date\ of\ last\ relapse-free\ disease\ assessment - date\ of\ first\ CR,\ CRi,\ CRh,\ CR_{MRD-},\ MLFS\ or\ PR + 1.$

No formal statistical analysis will be performed on anti-leukemic parameters.

Anti-leukemic activity data will be collected throughout Part 1 and Part 2 and will be summarized by cohort, by dose and overall.

Measures of anti-leukemic activity will be computed on both safety and efficacy populations and they will include:

- Changes (absolute and %) in pre- and post-treatment levels of leukemic blasts in the peripheral blood and/or bone marrow;
- Number and percentages of patients who reported as best overall response one of the following: CRM RD-, CR, CRh, CRi, MLFS, PR, SD, PD;
- Duration of response (DoR);

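### The SAP gives EFS two conflicting event lists: disease progression counts in the 12.1 formula but not in 5.4.2 or the 12.1 condition line, so median EFS depends on the paragraph programmed

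*SAP*

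**What the plan says.** SAP 5.4.2 (Secondary endpoints) runs EFS from first study drug intake "until the date of documented relapse, treatment failure or death from any cause". It does not list progression and does not define treatment failure. Its censoring rule is: "For a subject who did not experience the event, EFS is censored at the date of last relapse-free disease assessment".

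SAP 12.1 (Efficacy analysis) has three parts for EFS:

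- The condition line repeats the 5.4.2 list: "In case of relapse, treatment failure or all-cause death".
- The formula beneath it takes the earliest of relapse, disease progression, treatment failure or death. It defines treatment failure as no CR, CRh, CRi or CRMRD- after at least five cycles.
- The censoring line uses the last assessment free of relapse, treatment failure and progression.

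SAP 11.3 (Data imputation) sets one rule for RFS, EFS and DoR together: "the censoring date is defined as the date of the last relapse/progression/event-free disease assessment".

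The protocol names EFS as a Part 2 secondary measure (Table 2 and Section 8.9) but does not define it. SAP 11.2 summarises time-to-event variables by Kaplan-Meier curves, with the median and its 95% confidence interval. Table 3.3 is to be produced on both the efficacy and the safety populations.

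**The concern.** In relapsed or refractory AML, many patients can be expected to progress without ever reaching remission. Whether that progression is an EFS event largely determines what EFS measures. If it counts, EFS describes disease control. If it does not, EFS for these patients moves towards time to death.

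The SAP supports both readings and has no rule saying which section prevails. Two programmers working from the same document could report different medians. In an open-label, single-arm study, a choice made after the data are visible would also be hard to defend.

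A second, smaller matter is that no wording makes stopping treatment without response an event before five cycles are complete.

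**Working it through.** **1. The earliest date for non-response as failure.** The protocol synopsis states: "SEL24/MEN1703 is taken orally once daily (QD) for 14 consecutive days over a 21-day treatment cycle". Five cycles × 21 days = 105 days. Under the 12.1 formula, non-response alone cannot be treatment failure before about day 105.

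**2. One patient followed through each text.** Take a patient who never reaches CR, CRh, CRi or CRMRD-, progresses on day 60 and stops. Protocol Appendix D defines hematologic relapse only after one of those remissions, so this is not relapse. Fewer than five cycles have been given, so it is not treatment failure as 12.1 defines it.

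| Text applied | If the patient later dies | If alive at last contact |
|---|---|---|
| 12.1 formula | Event, day 60 | Event, day 60 |
| 12.1 condition line read strictly, then formula | Event, day 60 (death opens the event branch; the formula takes the earliest date) | Censored at the last progression-free assessment, before day 60 |
| 5.4.2 | Event at death | Censored at the last relapse-free assessment |

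A patient who never remitted cannot relapse. Every assessment is then relapse-free, so the 5.4.2 censoring date can fall on or after the progression itself.

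**3. Direction.** The formula's event list contains the 5.4.2 list plus progression, so each patient's event date under the formula is the same or earlier. If every patient is followed to an event, the 5.4.2 median cannot be the shorter one. Early censoring can break this ordering in a small cohort.

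**4. A hand-checkable example (invented data, 20 patients).**

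- Two responders relapse on days 200 and 260.
- One non-responder is treated through day 105.
- Two patients die on days 20 and 35.
- Seven progress and stop on days 30, 45, 45, 60, 60, 75 and 90.
- Eight stop without progression on days 15, 20, 25, 30, 40, 50, 60 and 70.
- All 15 in the last two groups die 60 days after progressing or stopping.

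All 20 have events, so the Kaplan-Meier curve reaches 0.5 at the tenth.

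- 12.1 formula: 20, 30, 35, 45, 45, 60, 60, 75, 75, **80**.
- 5.4.2, borrowing the five-cycle failure rule: 20, 35, 75, 80, 85, 90, 90, 100, 105, **105**.
- 12.1 formula with stopping counted as failure: 15, 20, 20, 25, 30, 30, 35, 40, 45, **45**.

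The choice of paragraph moves this median by 105 − 80 = 25 days. Not counting stops adds 80 − 45 = 35 days.

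**5. Simulation under assumed rates.** The documents give no EFS median, response rate or time to stopping, so there is no plan figure to reproduce. The assumptions were:

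- response rate 10% or 20%;
- mean time to progression 60 days;
- mean time to stopping without progression 40, 80 or 160 days;
- mean survival after stopping 90 or 150 days;
- follow-up after stopping 0, 30 or 365 days;
- marrow on day 43, then every 42 days;
- later progression picked up in 0% or 50% (50% only with 365-day follow-up).

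These make 48 scenarios, each with 20,000 patients.

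| Rule | Median EFS, range (days) | Difference within scenario (days) |
|---|---|---|
| 5.4.2, treatment failure left undefined | 70–127 | 30–92 longer than 12.1 formula |
| 5.4.2, five-cycle failure rule borrowed | 70–120 | 30–78 longer than 12.1 formula |
| 12.1 formula | 24–68 | – |
| 12.1 formula, non-responder stop counted at stop date | 16–37 | 4–47 shorter than 12.1 formula |

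For four of the scenarios, 1,500 cohorts of 20 were simulated. The 5.4.2 median (failure undefined) exceeded the 12.1 median in 88% to over 99% of cohorts and was shorter in 0% to 5%. The 12.1 median exceeded the stop-counted median in 78% to 97%, equalled it in 3% to 19% and was shorter in 0% to 8%. In both comparisons the reversals arose only with no follow-up after stopping.

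**The case against.** The strongest reply is that 12.1 is the operative derivation and 5.4.2 only a summary. Section 5.4.2 cannot be programmed alone because it leaves treatment failure undefined. The 12.1 formula, its censoring line and 11.3 agree with one another, so a careful programmer would probably count progression. That stands as a prediction, and it is why the fix follows the formula. It does not remove the conflict: 5.4.2 is the stated endpoint definition, the contrary list reappears in the condition line directly above the formula, and the 11.3 wording is shared by three endpoints.

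A reader might infer more than the text supports in three ways.

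- **That a non-responder who stops early has no event until death.** This is not so under 12.1. Protocol 3.6 and Table 5 footnote 18 provide follow-up of disease status about every three months for up to one year or until End of Study, partly to date progression. Progression recorded after stopping is still an event under the formula.
- **That Appendix D is a further EFS definition.** Its primary-refractory entry, "after 2 courses of intensive induction treatment", belongs to a general response table. Patients here must be unsuitable for intensive chemotherapy and receive a single oral agent.
- **That leaving discontinuation out of the events is an error.** It is a choice of estimand. Counting every stop without CR, CRh, CRi or CRMRD- would fail patients who withdraw consent, patients in MLFS (who count towards ORR) and possibly patients who stop for transplant.

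**Conclusion.** The SAP is wrong as written on one point: its EFS event lists disagree about progression, and the disagreement recurs inside 12.1. It affects patients who progress before completing five cycles without having reached remission. The expected direction is a longer median under 5.4.2. This follows from the event lists when follow-up is complete and is very likely, though not certain, in a cohort of about 20.

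The size cannot be derived from the documents. The 30 to 92 days rests wholly on assumed rates and should be read as showing that the choice can matter, not as a forecast. For the same reason, the documents do not support a flat statement that EFS will be too long because early stops are not counted. That holds only relative to an endpoint that counts them, and the excess could be as little as 4 days under the same assumptions.

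Severity is minor to moderate. EFS is secondary and descriptive, and no test, sample size, stopping rule or primary conclusion depends on it.

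**What to change.** Use one EFS definition in 5.4.2, 11.3 and the 12.1 condition line, matching the 12.1 formula:

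- **Event:** the earliest of relapse, disease progression, treatment failure or death from any cause.
- **Treatment failure:** no CR, CRh, CRi or CRMRD- after at least five cycles, dated at that assessment.
- **Censoring:** the last assessment free of relapse, progression and treatment failure. Keep the existing rule that EFS is not censored at transplant.

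Add one sensitivity analysis that counts permanent discontinuation without response as treatment failure at the stop date. State in advance whether MLFS and PR count as response there, and how stops for transplant are handled.

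The cost is SAP wording and one extra derivation, with no new data. The reported EFS may be less favourable than under 5.4.2.

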### 3.4. Reasons for Withdrawal of Patient from Study

Throughout the study, treatment with SEL24/MEN1703 may continue until the occurrence of one of the following events, whichever comes first:

- Patient withdrawal of consent.
- Disease progression.

*Note: Patients with disease progression may continue to receive SEL24/MEN1703, if in the opinion of the Investigator, they remain clinically stable and may be deriving*

*potential clinical benefit from SEL24/MEN1703 and it is not considered detrimental to the patient to continue study treatment.*

- Treatment delay of more than 2 weeks for reasons other than toxicity (see [Section 4.4](#)).
- Occurrence of an unacceptable toxicity (see [Section 4.4](#)).
- Requirement for treatment with prohibited medication (see [Section 6.9.3](#)).
- Treatment non-compliance.

*Note: Treatment non-compliance will be based on patient enquiry and SEL24/MEN1703 capsule count on return of used investigational medical product (IMP) to site. In Part 1 it will be defined as missing more than 2 doses in a 14-day dosing schedule in Cycle 1. After Cycle 1 and throughout Part 2, treatment compliance will be assessed on a case-by-case basis (see also [Section 4.4](#)).*

- Study non-compliance.
- Note: Each patient's continued willingness to attend study visits and undergo study assessments will be assessed on a case-by-case basis.*
- Investigator decision that it is in the patient's best interest to withdraw from the study.

Where appropriate (e.g. in the case of disease progression), continuation of the study treatment will be discussed between the Investigator and the Sponsor on a case by case basis. The DMC may also advise on the suitability of an individual patient to continue to receive study treatment.

Patients who experience a DLT will be permitted to receive further treatment with SEL24/MEN1703 according to the dose modification criteria described in [Section 4.4](#).

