11.2. Descriptive statistics

All study variables will be presented by cohort, dose and overall, by using the appropriate descriptive statistics according to the variable nature, unless otherwise specified:

- **Continuous variables:** number of non-missing observations, arithmetic mean, median, standard deviation (SD), minimum, maximum;
- **Categorical variables:** number of non-missing observations and column percentages (N, %);
- **Time to event variables:** number of non-missing observations, number and percentage of censored observations, 1st quartile, median and its 95% Confidence Interval (CI), 3rd quartile, Kaplan-Meier survival curves.

The behaviour over time of study variables will be summarised by cohort and overall as follows:

- **Continuous variables:** descriptive statistics for each time point of interest;
- **Discrete variables:** descriptive statistics for each time point of interest.

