11.5.6. Safety laboratory tests

An overall summary table of clinical chemistry, haematology, coagulation, lipid profile, bone marrow and urinalysis parameters by Visit, cohort, dose and time-point will be provided in the TLFs. The change from baseline will be summarized for each post baseline visit with descriptive statistics by cohort.

12. Efficacy evaluations

Disease assessment will involve evaluation of leukemic blast proportion in the bone marrow.

Hematologic parameters from the routine local assessments including blast percentage (where applicable), absolute neutrophil count (ANC), platelet count, and other relevant parameters such as transfusion dependence will also contribute to this assessment. Evaluation of disease status will be performed at the time-points described in the Schedule of Study Assessment (Table 5). To note, disease assessment must be performed as soon as the peripheral lab results become consistent with an objective response. Disease assessment will also include an aliquot of bone marrow aspirate/biopsy that will be centrally stored for future analysis (e.g. minimal residual disease), if any.

In case bone marrow aspirate/biopsy is consistent with CRi or better response, but still a minimal percentage of peripheral blasts is detected, the response assessment can be postponed up to 2 weeks and will be based on repeated peripheral blood results and last bone marrow aspiration results.

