 Table 2.3.4: Serious Adverse Events leading to Drug Interruption by System Organ Class and Preferred Term
 Table 2.3.5: Serious Adverse Events leading to Drug Reduction by System Organ Class and Preferred Term
 Table 2.4.1: Serious and Related Adverse Events by System Organ Class and Preferred Term
 Table 2.4.2: Serious and Related Adverse Events by Grade, System Organ Class and Preferred Term
 Table 2.4.3: Serious and Related Adverse Events leading to Drug Withdrawn by System Organ Class and Preferred Term
 Table 2.4.4: Serious and Related Adverse Events leading to Drug Interruption by System Organ Class and Preferred Term
 Table 2.4.5: Serious and Related Adverse Events leading to Drug Reduction by System Organ Class and Preferred Term
 Table 2.5.1: Dose Limiting Toxicity by System Organ Class and Preferred Term
 Table 2.5.2: Adverse Events leading to Death by System Organ Class and Preferred Term
 Table 2.5.3: Related Adverse Events leading to Death by System Organ Class and Preferred Term
 Table 2.6: Overall summary of Haematology Laboratory Parameters by Visit
 Table 2.6.1: Change vs Baseline of Haematology Laboratory Parameters by Visit
 Table 2.6.2: Shift Table for Haematology Laboratory Parameters
 Table 2.7: Overall summary of Clinical Chemistry Laboratory Parameters by Visit
 Table 2.7.1: Change vs Baseline of Clinical Chemistry Laboratory Parameters by Visit
 Table 2.7.2: Shift Table for Clinical Chemistry Laboratory Parameters
 Table 2.8: Overall summary of Coagulation Laboratory Parameters by Visit
 Table 2.8.1: Change vs Baseline of Coagulation Laboratory Parameters by Visit
 Table 2.9: Overall summary of Lipid Panel Parameters by Visit
 Table 2.9.1: Change vs Baseline of Lipid Panel Parameters by Visit
 Table 2.10: Overall summary of Bone Marrow Laboratory Parameters by Visit
 Table 2.11.1: Change vs Baseline of Bone Marrow Laboratory Parameters by Visit
 Table 2.12: Overall summary of Urinalysis Laboratory Parameters by Visit (Categorical Variables)
 Table 2.12.1: Overall summary of Urinalysis Laboratory Parameters by Visit (Continuous Variables)
 Table 2.13: Overall summary of Echocardiogram by Visit
 Table 2.14: Overall summary of ECG by Visit
 Table 2.14.1: Change vs Baseline of ECG by Visit
 Table 2.15: Overall summary of ECOG Performance Status by Visit
 Table 2.16: Overall summary of Physical Examination Parameters by Visit
 Table 2.17: Overall summary of Vital Signs by Visit

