13.2.3. Figures

Figures

- Figure 1: Overall Mean and Median timecourse – ALT ($\mu\text{kat/L}$)
- Figure 2: Overall Mean and Median timecourse – AST ($\mu\text{kat/L}$)
- Figure 3: Overall Mean and Median timecourse – Blasts ($10^9/\text{L}$)
- Figure 4: Overall Mean and Median timecourse – Hemoglobin (g/L)
- Figure 5: Overall Mean and Median timecourse – Lymphocytes ($10^9/\text{L}$)

Figure 6: Overall Mean and Median timecourse – Neutrophils ($10^9/L$)
Figure 7: Overall Mean and Median timecourse – Platelet ($10^9/L$)
Figure 8: Overall Mean and Median timecourse – White Blood Cells ($10^9/L$)
Figure 9: Overall Mean and Median timecourse – Total Bilirubin ($\mu mol/L$)
Figure 10: Overall Mean and Median timecourse – Direct Bilirubin ($\mu mol/L$)
Figure 11: Overall timecourse – ALT ($\mu kat/L$)
Figure 12: Overall timecourse – AST ($\mu kat/L$)
Figure 13: Overall timecourse – Blasts ($10^9/L$)
Figure 14: Overall timecourse – Hemoglobin (g/L)
Figure 15: Overall timecourse – Lymphocytes ($10^9/L$)
Figure 16: Overall timecourse – Neutrophils ($10^9/L$)
Figure 17: Overall timecourse – Platelet ($10^9/L$)
Figure 18: Overall timecourse – White Blood Cells ($10^9/L$)
Figure 19: Overall timecourse – Total Bilirubin ($\mu mol/L$)
Figure 20: Overall timecourse – Direct Bilirubin ($\mu mol/L$)
Figure 21: Individual MEN1703 PK concentration-time profiles (separate)
Figure 22: MEN1703 PK concentration-time profiles (mean values with error bars)
Figure 23: Boxplots of MEN1703 C_{max} and AUC_{24} at Cycle 1 Day 1 and at Cycle 1 Day 14, versus dose
Figure 24: Individual MET3 PK concentration-time profiles (separate)
Figure 25: MET3 PK concentration-time profiles (mean values with error bars)
Figure 26: Boxplots of MET3 C_{max} and AUC_{24} at Cycle 1 Day 1 and at Cycle 1 Day 14, versus dose

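### By-visit blast means and medians lose patients as they progress, so they lean towards apparent benefit; add one blast-change value per patient

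*SAP*

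**What the plan says.** SAP 12.1 puts changes "in pre- and post-treatment levels of leukemic blasts in the peripheral blood and/or bone marrow" at the head of the list of activity measures. That sentence does not say how the changes are laid out in time. Other sections do:

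- SAP 11.2 summarises behaviour over time by "descriptive statistics for each time point of interest".
- SAP 11.5.6, which covers haematology and bone marrow, adds: "The change from baseline will be summarized for each post baseline visit with descriptive statistics by cohort". SAP 11.5 says the same.
- The table index in SAP 13.2.1 carries this out in Table 2.6.1 for haematology and Table 2.11.1, "Change vs Baseline of Bone Marrow Laboratory Parameters by Visit".
- SAP 13.2.3 plots blasts (10⁹/L) in "Figure 3: Overall Mean and Median timecourse".

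On missing data, SAP 11.3 states: "The missing values will not be imputed because, for all the analyses, an observed-cases approach will be applied".

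Protocol 3.4 says that treatment "may continue until the occurrence of one of the following events, whichever comes first", and disease progression is on that list. A note lets a clinically stable patient continue past progression at the investigator's discretion. Appendix D defines progression mainly by blasts. One criterion is a rise of more than 50% in marrow blasts, with at least 15 points if baseline is below 30%. Another is a rise of more than 50% in peripheral blasts to above 25 × 10⁹/L.

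Peripheral blasts are due at Day 14 of each cycle and at the Final Study Visit (Table 5, footnote 5). Marrow samples after C3D1 are recommended rather than mandatory, and the Final Study Visit marrow may be skipped in progressive disease (footnote 7).

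**The concern.** The event that removes a patient from later treatment visits is, for the most part, a rise in the quantity being averaged. An observed-case mean or median at Cycle 3 or 4 therefore describes those who have not yet progressed, not those who were treated. With a single arm, no control curve shares the same selection, so a reader cannot separate drug effect from attrition by looking at Figure 3 or the change-from-baseline tables.

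The efficacy population adds a little to this. It requires a completed first cycle and at least 75% of the drug in that cycle (SAP 7.3), so early failures are gone before the first point is drawn. The safety-population version does not have that extra step.

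No efficacy table in SAP 13.2.1 is titled as blast change. The by-visit laboratory outputs and Figure 3 are thus where a reader would look for the first-listed activity measure, and the SAP gives no caution about reading them as activity.

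**Working it through.** The plan states no figure on this point, so there is nothing to reproduce. The check asks how an observed-case summary behaves when the drug does nothing. All growth, spread and error inputs below are assumptions.

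**Peripheral blasts, simple exit rule.** Let log₂(blasts at day t ÷ baseline) = s·t/21 + e. Here s is a patient's growth in doublings per 21-day cycle, with mean g and SD 0.7, and e is noise with SD 0.3. Visits are Day 14 of Cycles 1 to 4 (t = 14, 35, 56, 77). Patients leave after a value above 1.5 × baseline. The full-cohort median change is 2^(g·t/21) − 1. For g = 0.3:

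| Visit | Full cohort | Observed cases |
|---|---|---|
| C1D14 | 2^0.2 − 1 = +15% | +15% |
| C2D14 | 2^0.5 − 1 = +41% | +11% |
| C3D14 | 2^0.8 − 1 = +74% | −26% |
| C4D14 | 2^1.1 − 1 = +114% | −48% |

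The median of each patient's last observed value is +61%. With g = 0, the observed C4D14 median is −61% against a true 0%.

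The result is sensitive to the inputs. At g = 0.3 the observed C4D14 median becomes −27% if the between-patient SD is 0.5, and +5% if it is 0.3. With SD 0.7 it is −15% if 30% of progressors stay on drug and +14% if 50% do.

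**Peripheral blasts, Appendix D threshold added.** The 1.5 × rule alone is too quick an exit, because the peripheral criterion also requires more than 25 × 10⁹/L. Baseline is assumed lognormal (log-SD 1, capped at 30 × 10⁹/L), SD 0.7, and all progressors leave. Observed C4D14 medians (repeat runs differ by one or two points):

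| Assumed median baseline (10⁹/L) | g = 0.3 (true +114%) | g = 0 (true 0%) |
|---|---|---|
| 1 | +91% | −5% |
| 3 | +49% | −19% |
| 8 | −1% | −38% |
| 15 | −24% | −49% |

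Every entry is below the truth, but the sign and size depend on a baseline level that the documents do not give.

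**Marrow blasts, Appendix D marrow rule.** Baseline is uniform from 20% to 80%. Each patient has a linear slope with mean μ and SD τ (points per assessment), and measurement SD is 5 points. All progressors leave. Mean change at the fourth assessment, observed (full cohort):

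| μ | τ = 5 | Gap | τ = 10 | Gap |
|---|---|---|---|---|
| 0 | −3.2 (0.0) | −3.2 | −10.5 (0.0) | −10.5 |
| +2 | +2.6 (+7.4) | −4.8 | −6.5 (+5.9) | −12.4 |
| +4 | +8.0 (+14.8) | −6.8 | −2.7 (+11.7) | −14.4 |
| +6 | +12.9 (+21.6) | −8.7 | +1.0 (+17.3) | −16.3 |
| +10 | +20.6 (+33.5) | −12.9 | +8.1 (+27.3) | −19.2 |

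The gap is always negative. The observed mean drops below baseline in four of the ten cells: both with no growth, and τ = 10 with μ = +2 or +4. In the last of these the median is +0.2, so it does not fall. There is no bias at the first assessment. It is modest at the second: for τ = 10 the gap is −1.6 points at μ = 0 and 13.9 − 18.3 = −4.4 at μ = +10. If 30% of progressors are treated past progression, the no-growth means shrink to −2.2 (τ = 5) and −6.8 (τ = 10). If all are, the bias vanishes.

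**The case against.** A reader might infer that mean and median blasts must fall over time whatever the drug does. The documents do not support that. The protocol's introduction calls AML extremely aggressive, and with brisk growth (+6 or +10 points per assessment in the marrow model) the observed mean and median rise under an inert drug; they only rise too little. Nor do the summaries contain only patients still on treatment. Treatment past progression is allowed, and peripheral blasts are due at the Final Study Visit. That value is reported as its own visit, however, so it does not repair the on-treatment points.

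Other objections also have force. SAP 11.2 already gives the number of non-missing observations with each continuous summary, so the shrinking denominator will be visible in the tables. Figure 13 is a separate blast time course that may show individual trajectories, and the listings hold patient-level haematology, marrow and response. Figure 3 sits among laboratory plots such as ALT and haemoglobin and is not labelled as an efficacy figure. No test or decision rule uses the curve. Best overall response (including PD), DoR, RFS, EFS and OS stand beside it, and EFS counts progression directly.

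These points limit the consequence and rule out any confident percentage. They leave the direction of the bias intact, and they do not supply a per-patient summary of the first-listed activity measure.

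**Conclusion.** The concern holds as a statement about direction. By-visit observed-case blast summaries are biased towards apparent benefit from the second assessment onwards, and may fall with an inactive drug. This rests on two features of the documents: progression normally ends treatment, and it is defined largely by rising blasts. Size depends on growth rate, between-patient spread, baseline level and the share treated past progression. The documents give none of these, so the figures above are illustrations, not estimates for this trial.

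Because the measure is descriptive and secondary, no primary conclusion is at risk. This is an inexpensive improvement to how activity is shown.

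**What to change.** In SAP 12.1 and 13.2, add an efficacy table and a waterfall plot, by cohort and dose and separately for blood and marrow. Each should carry one value per treated patient who has a baseline and a post-baseline blast value:

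- **Main summary:** last on-treatment change, replaced by the Final Study Visit or progression-visit value where that is later, with progressors flagged.
- **Supplement:** best change, labelled as favourable by construction.

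Keep the by-visit tables and Figure 3. Print the number of patients contributing at each visit on Figure 3, and state in SAP 12.1 that by-visit means and medians do not estimate drug activity.

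The last-change summary is less exposed to this selection but not free of it. In the first model its median was +61%, against −48% for observed cases and +114% for the full cohort at C4D14. Marrow values will also remain incomplete where the Final Study Visit sample is skipped.

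The cost is SAP wording, one table and one figure, and probably a less favourable-looking activity summary. No new data are needed.
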